10.3.2.2. Treatment Policy Estimand

Analyses based on the treatment policy estimand will describe outcomes from index through the end of the follow-up period for both the Roctavian Cohort and SoC Cohort. A participant's time in the analysis will only be censored in the event of a withdrawal, loss to follow-up, death or enrollment in an interventional trial. Follow-up will be censored based on the earliest date after index of withdrawal, loss to follow-up, enrollment into an interventional clinical trial, death (inclusive of date of death), end of reporting/follow-up period in the DHR, or end of study follow-up (eg, index date +3 years). Due to the non-interventional nature of the study and AbD, a participant in the SoC Cohort may subsequently receive Roctavian during follow-up after the recruitment period, if this occurs this participant will be excluded from the analysis. If a participant in the Roctavian Cohort returns to prophylaxis with another hemostatic therapy (eg, exogenous FVIII or emicizumab), this participant will be maintained in the analysis (ie, not excluded from the analysis) as there is a potential continued benefit of the gene therapy after prophylaxis is resumed for effectiveness outcomes and potential long term risk of safety events associated with the gene therapy.

Outcomes for participants in the SoC Cohort who are treated with Roctavian during follow-up after the recruitment period, and are excluded from the analysis, will be described separately. Outcomes will be described for the period these participants were on SoC (index date to date of Roctavian infusion) and treated with Roctavian (date of Roctavian infusion through the end of follow-up).

[Figure 2](#) below illustrates the treatment policy estimand analysis.

Figure 2: Analysis Schema for Treatment Policy Estimand

[figure not shown]

Figure note: Outcomes described from index through the end of the follow-up period for both the Roctavian Cohort and SoC Cohort. A participants’ time in the analysis will only be censored in the event of a withdrawal, loss to follow-up, death or enrollment in an interventional trial (based on earliest date of). Any participant in the SoC Cohort who subsequently receives Roctavian during follow-up after the recruitment period will be excluded from the analysis.

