10.3.2.3. Hypothetical Estimand

Analyses based on the hypothetical estimand will describe outcomes during the follow-up period for both the Roctavian Cohort and SoC Cohort, minimizing time periods during which outcomes are confounded by exposure to both gene therapy and SoC prophylaxis. As PwSHA administered Roctavian will remain on prophylaxis for a time following the index date as endogenous FVIII production initiates, the analytical follow-up period for outcomes such as bleeding events and hemostatic therapy utilization for the Roctavian Cohort will begin 5 weeks post-infusion or 3 days after the end of routine FVIII prophylaxis (whichever occurs later), or 27 weeks after end of emicizumab prophylaxis consistent with analyses of the Roctavian clinical trials. The analytical follow-up period of the SoC Cohort will begin on the index date. Participants in the Roctavian Cohort will be censored at the time of resumption of SoC prophylaxis and participants in the SoC Cohort who subsequently receive Roctavian during follow-up after the recruitment period, will be censored on the date of Roctavian infusion. As with the treatment policy estimand, for both cohorts a participant’s time in the analysis will be censored in the event of a withdrawal, loss to follow-up, death or

enrollment in an interventional trial. Follow-up will be censored based the earliest date after index of any of the censoring events described above.

Figure 3 below illustrates the hypothetical estimand analysis.

Figure 3: Analysis Schema for Hypothetical Estimand

[figure not shown]

Figure note: For the Roctavian Cohort, analytical follow-up period for outcomes such as bleeding events and hemostatic therapy utilization will begin on 5 weeks post-infusion or 3 days after the end of routine FVIII prophylaxis (whichever occurs later), or 27 weeks after end of emicizumab prophylaxis consistent with analyses of the Roctavian clinical trials. Participants in the Roctavian Cohort will be censored at the time of resumption of SoC prophylaxis. For the SoC Cohort, analytical follow-up period of the SoC Cohort will begin on the index date. Participants in the SoC Cohort who subsequently receive Roctavian during follow-up after the recruitment period, will be censored on the date of Roctavian infusion.

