10.3.6. Primary Objective

10.3.6.1. Objective: To compare the annualized bleeding rate for treated bleeds.

Annual bleeding rates for treated bleeding events (see [Table 6](#)) will be compared between the Roctavian Cohort and SoC Cohort after PS adjustment. *A priori* the PS adjustment is planned to be implemented via IPTW. All participants with the variables recorded to derive the PS will be included in the analysis. Participants with no bleeds reported but data entered into the DHR will have an ABR of zero (ie, data is not considered missing).

ABRs will be compared over the full follow-up time for each participant in the study, as well as during annual increments during the follow-up. For analyses of annual increments, only those participants who have full follow-up for the time will be included in analyses. For example, analyses comparing ABRs during the first year will only include participants with ≥ 1 year of follow-up after the index date or analyses comparing ABRs through 2 years of follow-up will only include participants with ≥ 2 year of follow-up after the index date.

Sample sizes are expected to be reduced in analyses of annual increments for interim analyses as data collection will be ongoing, and potentially reduced for final analyses due to censoring (see below).

ABRs will be calculated for each participant as the number of bleeds divided by the time between the start of follow-up and censoring event for the analysis, annualized to the number in 1 year. The mean of the individual participant ABRs for each cohort will be calculated and compared. The primary comparison of ABRs will be based on the absolute difference in the mean treated ABR between the Roctavian Cohort and SoC Cohort utilizing a two-sample t-test (two-sided).

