10.3.7. Secondary Objectives

10.3.7.1. Objective: To compare the annualized bleeding rate for major, life threatening, and joint bleeds.

ABRs for other bleeding outcomes described in [Table 6](#) (major bleeds, life-threatening bleeds and joint bleeds) will also be compared between the Roctavian Cohort and SoC Cohort after PS adjustment. The analysis approach will be consistent with the primary objective (see Section [10.3.6](#)) regarding PS adjustment approach, analysis of the full follow-up time along with annual increments, as well as measurement of treatment effect.

10.3.7.2. Objective: To compare the proportion of participants with zero bleeds for treated, major, life threatening, and joint bleeds.

Proportion of participants with zero bleeding events for all bleeding outcomes described in Table 6 will be compared between the Roctavian Cohort and SoC Cohort after PS adjustment, generally consistent with the analysis approach for ABRs (see Section 10.3.6 above) regarding PS adjustment approach, analysis of the full follow-up time along with annual increments, as well as, start of bleed follow-up and censoring reasons.

Differing from the approach for ABRs, analyses of the proportion of participants with zero bleeding will only include those participants with follow-up for the full time over which the proportion is calculated. Additionally, the measurement of treatment effect for these analyses will be the relative risk and 95% confidence interval between participants in the Roctavian Cohort and SoC Cohort having zero bleeding events.

10.3.7.3. Objective: To compare the use of hemostatic medications.

The use of hemostatic medications will be compared between the Roctavian Cohort and SoC Cohort after PS adjustment, generally consistent with the analysis approach for ABRs (see Section 10.3.6 above) regarding PS adjustment approach, and analysis of the full follow-up time along with annual increments. Comparisons will be made regarding the variables in Table 7.

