Descriptive statistics will be used to summarize the absolute and change from baseline at the time of an assessment for the total and domain scores for the Haemo-QoL-A and the BPI-SF. For the BPI-SF the pain interference and pain intensity scores will be taken as the domains. A repeated measurement analysis model will be used to compare the changes in scores between the treatment groups. Participants with an evaluable baseline score and at least one evaluable post-baseline score will be required for the specific analysis be included in the change from baseline analyses.

In addition, responder analyses will be considered for improvement and deterioration for the BPI-SF pain interference and pain intensity scales. The BPI-SF pain intensity score will be defined as the Question 5 “average pain”. The BPI-SF pain interference score will be defined as the average to all 7 subitems of Question 9 (9A to 9G).

All analysis details and scoring methods will be described in the SAP. It is expected that no missing data will be imputed.

All PROs comparisons will be interpreted after 3 years of follow-up, or latest available follow-up score if a full 3 years of follow-up is not available.

10.3.7.5. Objective: To compare safety events of interest.

Safety events outlined in [Table 8](#) will be described in each cohort. Summaries of the proportion, event rate, and incidence rate of each of the safety events among all participants by cohort will be provided. Safety events will be described from index through follow-up. All participants will be included in analyses of event and incidence rates, while analyses of the proportion of participants will only include those participants with follow-up for the full time over which the proportion is calculated. Safety outcomes will be compared as relative risks based on the incidence of an event for analyses of the treatment policy estimand and as incidence rate ratios censoring a participants person time at the time of the event for analyses of the hypothetical estimand.

10.3.7.6. Objective: To describe time to resumption of prophylactic treatment among participants administered Roctavian

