7.9.4.5. Safety Events

Population	Measurement Period	Analysis Notes
All participants	All available follow-up data	
Safety events will be compared between the Roctavian and SoC Cohorts
 
Due to the possibility of unknown responses, there may be insufficient data to fully describe participant comorbidities that may confound the 'true' causal reason for an event.

Safety events outlined in Table 5 will be reported for both the Roctavian and SoC Cohorts.

Regarding the treatment policy estimand data analysis, the proportion of participants with each event will be calculated from index through the full follow-up period, without considering any intercurrent events. Given safety outcomes are event-based, for safety outcomes occur multiple times over the follow-up period (e.g., thromboembolic events), IPTW-weighted negative binomial regression models will be fit to compare safety outcomes between Roctavian and SoC Cohorts. For safety outcomes expected to occur once (e.g., death), IPTW-weighted log binomial regression models will be fit to compare safety outcomes between Roctavian and SoC Cohorts.

IPTW will be applied to create more similar Roctavian and SoC Cohorts. Other clinically significant prognostic factors or covariates that remain imbalanced after propensity score adjustment will be included in the model as well. Regression coefficients, corresponding 95% CIs and p-values will be reported for all explanatory variables included in the model. In the case that there are little to no events $n < 10$, that the relative risk log-binomial regression or negative binomial regression estimates are not stable, a logistic regression (which can approximate relative risk in a rare outcome⁵⁹) with firch correction will be conducted.

Under the hypothetical estimand data analysis, the event rate and incidence rate of each event will be calculated from index through the full follow-up period, where all participants will be included in analyses of event or incidence rates. Further, to compare Roctavian and SoC Cohorts safety outcomes under the hypothetical estimand, IPTW-weighted incident rate ratios (IRRs) will be estimated at the incident/event rate among the Roctavian Cohort divided by the incident/event rate among the SoC Cohort. See below for the event and incidence rate calculations:

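### The full-follow-up rule empties the death proportions by construction and, under the hypothetical estimand, drops from each bleeding window the Roctavian participants who resumed prophylaxis before it closed

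*Protocol*

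**What the plan says.** **Safety.** Protocol 10.3.7.5 first promises results for everyone: "Summaries of the proportion, event rate, and incidence rate of each of the safety events among all participants by cohort will be provided". It then separates two kinds of summary. For rates, "All participants will be included in analyses of event and incidence rates". For proportions, "analyses of the proportion of participants will only include those participants with follow-up for the full time over which the proportion is calculated". Under the treatment policy estimand, safety outcomes are compared as relative risks; under the hypothetical estimand, as incidence rate ratios.

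Section 10.3.2.2 lists the events that end follow-up under the treatment policy estimand. The list includes "death (inclusive of date of death), end of reporting/follow-up period in the DHR".

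SAP 7.9.4.5 gives all participants as the safety population. For the treatment policy estimand it says that "the proportion of participants with each event will be calculated from index through the full follow-up period", disregarding intercurrent events.

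**Bleeding.** Section 10.3.7.2 says that zero-bleed analyses "will only include those participants with follow-up for the full time over which the proportion is calculated", and presents this as a departure from the ABR approach. Annual ABRs have their own sentence in 10.3.6.1: "For analyses of annual increments, only those participants who have full follow-up for the time will be included in analyses". Section 10.3.2.3 (hypothetical estimand) adds: "Participants in the Roctavian Cohort will be censored at the time of resumption of SoC prophylaxis". Section 10.3.2.2 keeps such participants in the treatment policy analysis.

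**The concern.** A full-window requirement is harmless only if the reason for an incomplete window has nothing to do with the outcome. That fails in two places.

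For death, the outcome is itself the reason the window is incomplete. The comparison at risk is the relative risk under the treatment policy estimand, which the G-BA required. All-cause death, hemophilia-related death and fatal adverse events are listed outcomes. A participant with another safety event who dies inside the window is lost from that proportion as well.

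For bleeding under the hypothetical estimand, resumption of prophylaxis ends follow-up. Each window then holds only Roctavian participants who had not resumed by its end, which is selection on a post-index event that may well be related to bleeding. A participant who bled and was censored afterwards is also discarded, although he is already known not to be bleed-free.

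**Working it through.** **Planning figure.** No sample-size figure depends on these rules, but the planning inputs are reused below, so they were checked first. Inputs (Protocol 10.1, SAP 7.6): rates 3 (SoC) and 0.85 (Roctavian) per year, dispersion 1.5, allocation ratio 0.2, null ratio 0.5, mean exposure 1 year, one-sided 2.5%, power 80%.

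- V1 = 1/3 + 1/(0.2 × 0.85) + 1.2 × 1.5/0.2 = 15.216
- V0 (fixed marginal total) = 1.1²/(0.5 × 0.2 × 3.17) + 9 = 12.817
- N(SoC) = (1.960 × √12.817 + 0.842 × √15.216)² / (ln 0.5 − ln(0.85/3))² = 328.8; Roctavian 0.2 × 328.8 = 65.8

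Rounded up, 329 + 66 = 395 against the stated 397, which is close enough to reuse the inputs.

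**Deaths.**
1. A participant enters a safety proportion only if followed for the whole window (10.3.7.5).
2. Follow-up ends at death (10.3.2.2). Counting the day of death helps only a death on the last day of the window.
3. Otherwise nobody who dies inside the window is in the numerator or the denominator.

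The documents give no death risk, so the 3-year risks below are assumptions.

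| Assumed risk | Expected deaths of 70 Roctavian | Expected deaths of 330 SoC | Counted under the literal rule |
|---|---|---|---|
| 1% | 0.7 | 3.3 | 0 and 0 |
| 2% | 1.4 | 6.6 | 0 and 0 |
| 5% | 3.5 | 16.5 | 0 and 0 |

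A relative risk of these proportions is 0/0 in every row.

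**Who is dropped at resumption.** The rules work window by window. Someone who resumes in year 3 stays in the 1-year and 2-year windows and leaves only the 3-year one. If resumption times were uniform over 3 years (assumed), the 1-year window would keep 2/3 of resumers, the 2-year window 1/3 and the 3-year window none.

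**Zero bleeds at 3 years.** With negative binomial counts, P(0) = (1 + 1.5 × rate × t)^(−1/1.5).
- Roctavian: (1 + 1.5 × 0.85 × 3)^(−2/3) = 4.825^(−2/3) = 0.350
- SoC: (1 + 1.5 × 3 × 3)^(−2/3) = 14.5^(−2/3) = 0.168
- Risk ratio 2.08

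Let a share r resume by year 3 (assumed). The largest shift arises if every resumer had already bled, when the retained proportion is 0.350/(1 − r).

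| r | Roctavian zero-bleed after dropping | Risk ratio |
|---|---|---|
| 10% | 0.389 | 2.31 |
| 20% | 0.438 | 2.60 |
| 30% | 0.500 | 2.97 |

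These are upper bounds. If resumption is unrelated to bleeding, the proportion stays at 0.350.

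**Annual ABR.** If a share r is dropped and bleeds at k times the rate of the rest, the retained rate is 0.85/(1 − r + rk). For r = 20% this is 0.85, 0.71 and 0.61 at k = 1, 2 and 3, against 0.85 for everyone.

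**The case against.** **Deaths.** The same paragraph promises proportions for all participants, and rates include everyone. The relative risk is described as based on incidence, without naming the restricted proportions. SAP 7.9.4.5 uses all participants and a log-binomial model for death, and shell Table 15 has death rows. All of this stands. A reader might infer that the plan loses deaths altogether; it does not, because the rates count them. But these texts contradict the restriction rather than cure it, and an analyst who follows the restriction gets an empty comparison.

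**Bleeding.** Four stronger readings are tempting and not supported.
- That every resumer disappears from all zero-bleed and annual ABR results: this is true only of the 3-year window.
- That a single rule on proportions governs both: the annual ABR exclusion is a separate sentence in 10.3.6.1.
- That SoC keeps everyone: SoC participants who receive Roctavian after recruitment are censored at infusion under the same estimand, and withdrawal, loss to follow-up and trial entry apply to both cohorts.
- That the bias certainly favours Roctavian: this depends on a link between resumption and bleeding that the documents do not quantify.

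A reader might also infer that the delayed analytical start inflates one-year zero-bleed from 58% to 73%. That needs 27 weeks of lost risk time, which concerns only prior emicizumab users, and needs windows counted from index. With the 5-week minimum after FVIII, the same formula gives about 60%.

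SAP 7.9.4.2 also lists zero bleeds over all available follow-up. This helps only in part: participants censored early have had less time in which to bleed, and 10.3.7.2 rules out unequal follow-up.

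**Conclusion.** The point holds in two parts of different weight.

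The safety part is a contradiction with a definite result. Followed literally, 10.3.7.5 combined with 10.3.2.2 gives death and fatal-event proportions of zero at any death risk, an undefined relative risk wherever it is built on them, and other safety proportions stripped of participants who died. This needs no assumption beyond the wording. It should be settled before any comparative report.

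The bleeding part is a conditional bias, confined to the hypothetical estimand and to windowed analyses. It favours Roctavian if resumption is commoner in those who bleed, and is absent if the two are unrelated. With 10-30% resuming, the 3-year zero-bleed risk ratio of 2.08 could rise to between 2.31 and 2.97 at most. Those shares are assumed, and the documents do not allow the size to be fixed. The full-follow-up ABR has no full-window restriction, and the treatment policy results keep resumers. The affected outcomes other than the annual ABRs for treated bleeds are secondary, with nominal p-values (SAP 7.9).

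**What to change.** 1. **Safety proportions.** Delete the full-follow-up restriction in 10.3.7.5 and align the section with SAP 7.9.4.5. Keep all participants in the denominator, or report cumulative incidence with death as the event or, for other outcomes, as a competing event.
2. **Zero bleeds, hypothetical estimand.** Use all participants through propensity-weighted time to first bleed, with Kaplan-Meier estimates at 1, 2 and 3 years, so that bleeds seen before censoring count. Add a sensitivity analysis that treats resumption of prophylaxis as not bleed-free.
3. **Annual ABRs.** Include partial intervals with a log-time offset. State that censoring at resumption may still be informative: someone who resumed in year 1 contributes nothing to year 3 under this change either.

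The cost is rewording in Protocol 10.3.6 and 10.3.7 and SAP 7.9.3 to 7.9.4, and slightly more programming. No new data are required.

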4. STUDY OBJECTIVES AND ENDPOINTS

The aim of this non-interventional study is to evaluate the overall effectiveness and safety of Roctavian compared to SoC hemostatic prophylaxis treatments for PwSHA.

The specific objectives are listed below. All objectives will compare Roctavian and SoC with exogenous FVIII or emicizumab, unless otherwise noted.

Table 1: Objectives and Endpoints

[figure not shown]
Objectives	Endpoints
Primary	
To compare the annualized bleeding rate for treated bleeds.	
 Bleeding events requiring treatment with exogenous FVIII
Secondary	
To compare the annualized bleeding rate for major, life threatening, and joint bleeds.	
 Major bleeding events Life-threatening bleeding events Bleeding events occurring in the joint
To compare the proportion of people with zero bleeds for treated, major, life threatening, and joint bleeds.	
 Bleeding events requiring treatment with exogenous FVIII Major bleeding events Life-threatening bleeding events Bleeding events occurring in the joint
To compare the use of hemostatic medications.	
 Prophylactic hemostatic treatments On-demand hemostatic treatments
To compare joint health, quality of life, and pain.	
 Hemophilia Quality of Life assessment (Haemo-QoL-A) Hemophilia Joint Health Score (HJHS) Brief Pain Inventory-Short Form (BPI-SF)
To compare safety events of interest.	
 All cause death Hemophilia-related death Adverse events leading to hospitalization or death Targeted adverse events of development of FVIII inhibitors, thromboembolic events, new malignant neoplasms, and severe liver disease (liver failure or cirrhosis)
To describe time to resumption of prophylactic treatment among persons administered Roctavian.	
 Resumption of prophylactic hemostatic treatments

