7.2.5.2. Use of hemostatic treatments

Endpoints for secondary objectives regarding hemostatic therapy usage will be based on therapeutic usage of exogenous FVIII and emicizumab recorded in the DHR. Key endpoints for comparing use of hemostatic therapy, along with relevant variables collected in the DHR, are described in [Table 7](#). Use of any exogenous FVIII or emicizumab, the number of uses (stratified by prophylaxis vs on-demand/for bleed treatment), amount of exogenous FVIII consumed and number of infusions will be compared between cohorts. Endpoints will be compared based on the total follow-up, as well as specific periods of time starting from index date (eg, during the 2nd or 3rd year of follow-up). Details on the calculation of these outcomes based on the therapeutic usage recorded in the DHR are described further in [Section 10.3](#) and the SAP. Hemostatic therapy usage will be recorded from the index date through the follow-up period for each participant in the AbD.

For the Roctavian Cohort only, the proportion of participants who return to prophylactic hemostatic therapy, along with the time to return to prophylaxis will be described for those in the cohort who ended prophylaxis post Roctavian administration.

Table 7: Hemostatic Treatment During Follow-Up

Variable	Description	Captured in DHR	Time period for Analysis	Entry into DHR	Operational notes including Relevant Data Fields in DHR
Use of hemostatic treatments	Use of any hemostatic treatments	✓	Follow-up	Ongoing	Derived based on therapy usage recorded in the DHR for exogenous FVIII and/or emicizumab.
FVIII Consumption	FVIII consumption during follow-up	✓	Follow-up	Ongoing	Derived based on reported FVIII consumption for each therapeutic use of FVIII, reported for different prophylaxis types (see Table 4) and on-demand use. Will be described based on total FVIII utilized in international units (IUs), as well as IU/KG based on weight data (see Table 3). On demand use of FVIII will be defined as use of FVIII for suspected bleeding, spontaneous bleeding, traumatic, bleeding/bleeding, or intensified on-demand treatment (short-term prophylaxis).
Infusion/ Injection Rate	Number of infusions/ injections during follow-up	✓	Follow-up	Ongoing	Derived based on the therapy usage and frequency of use during individual usage periods recorded in the DHR for any reason and summarized as annualized infusion/injection rate (AIR).

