Return to prophylaxis	*For Roctavian Cohort only* Use of continuous prophylaxis	✓	Follow-up	Ongoing	Derived based on the recording of physician report of 'return to prophylaxis' in the DHR.

AIR, annualized infusion/injection rate; DHR, German Hemophilia Register; FVIII, Coagulation factor VIII; SAP, Statistical Analysis Plan.

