Time between Roctavian administration (index date) and resumption of hemostatic prophylaxis (defined in [Table 7](#)) will be described for the Roctavian Cohort only. The proportion who return to prophylaxis and time to resumption will be described among those in the cohort who ended prophylaxis post Roctavian administration. Summary statistics will

be utilized to describe time to resumption including mean (SD), median (inter quartile range), minimum and maximum. Treatment utilization patterns in the 3 and 6 months after the resumption of prophylaxis will be described regarding the number of infusions/injections by prophylaxis treatment class, total FVIII dose for participants returning to prophylaxis with FVIII, and frequency of infusions/injections will be described.

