7.9.4.6. Time to Resumption of Prophylactic Treatment

Population	Measurement Period	Analysis Notes
Roctavian Cohort only	All available follow-up data	Definition utilized in this study is relevant to the fields that the DHR collects and will be aligned as best as possible to other definitions utilized external to this study

For participants in the Roctavian Cohort, time to resumption of prophylactic treatment will be measured for participants who received SoC prophylaxis after Roctavian administration during the follow-up period. Treatment utilization patterns in the 3 and 6 months after the resumption of prophylaxis will be described regarding the number of infusions/injections by prophylaxis treatment class, total FVIII dose for participants returning to prophylaxis with FVIII, and frequency of infusions/injections. Summary statistics will be utilized to describe time to resumption including mean, SD, median, IQR, minimum, and maximum.

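### Roctavian recipients who never end prophylaxis are left out of the return-to-prophylaxis objective and have no follow-up start for bleeding and hemostatic-use outcomes under the hypothetical estimand

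*Protocol*

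**What the plan says.** Protocol Section 4, Table 1, gives the objective as: "To describe time to resumption of prophylactic treatment among persons administered Roctavian". The Roctavian Cohort (Protocol 10.2) is everyone infused during recruitment.

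Protocol 10.3.7.6 then sets the analysis population: "The proportion who return to prophylaxis and time to resumption will be described among those in the cohort who ended prophylaxis post Roctavian administration". Protocol 7.2.5.2 repeats the restriction: "time to return to prophylaxis will be described for those in the cohort who ended prophylaxis post Roctavian administration". The event itself is "Derived based on the recording of physician report of 'return to prophylaxis' in the DHR" (Table 7).

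Under the hypothetical estimand (Protocol 10.3.2.3, repeated in SAP 7.2.3), Roctavian follow-up for outcomes such as bleeding and hemostatic use begins "5 weeks post-infusion or 3 days after the end of routine FVIII prophylaxis (whichever occurs later), or 27 weeks after end of emicizumab prophylaxis". SoC participants enter at index. The treatment policy estimand (Protocol 10.3.2.2) follows both cohorts from index.

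SAP 7.9.4.6 words the resumption population differently: "for participants who received SoC prophylaxis after Roctavian administration during the" follow-up period. The Table 18 shell in SAP Annex 12.1 heads its column with the Roctavian Cohort as a whole.

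**The concern.** Protocol 10.3.2.1 says recipients continue prophylaxis in the initial weeks after infusion, so every recipient could in principle never stop. Someone who never stops cannot have a recorded return, and he is not in the set among whom returns are described. No section asks for a count of such people. An objective meant to show how long recipients stay free of prophylaxis therefore says nothing about those who never became free of it.

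The gap in the hypothetical estimand has the same origin. If prophylaxis never ends, no start date exists and no rule is given. The selection happens after index and in one arm only, so propensity weights built on baseline variables cannot correct it. This matters because Protocol 10.3.2.1 calls the hypothetical estimand the more clinically interpretable of the two.

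**Working it through.** **Who is in each analysis**

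| Analysis | Stopped, stayed off | Stopped, later returned | Never stopped |
|---|---|---|---|
| Return to prophylaxis (Protocol 10.3.7.6, 7.2.5.2) | denominator | numerator and denominator | absent |
| Hypothetical estimand, bleeding and hemostatic use | from the delayed start | from the delayed start until resumption | no start defined |
| Treatment policy estimand | from index | from index | from index |
| Safety (Protocol 10.3.7.5) | from index | from index | from index |

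**Effect on the return proportion.** The documents give neither a never-stopped rate nor a return rate, so both are assumed. Let N be infused, f never stopped and r the return proportion among stoppers. The plan reports r whatever f is. The share of all infused on continued or resumed prophylaxis is (r(N − f) + f)/N.

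- N = 70, r = 0.30: f = 4 gives (19.8 + 4)/70 = 34%; f = 7 gives (18.9 + 7)/70 = 37%; f = 10 gives (18 + 10)/70 = 40%.
- N = 67, r = 0.10: f = 3, 7, 10, 13 give 14.0%, 19.4%, 23.4%, 27.5%.
- N = 67, r = 0.20: the same f give 23.6%, 28.4%, 31.9%, 35.5%.
- f = 0 gives r, and nothing changes.

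If Table 18 instead divides returners by the whole cohort, never-stoppers count as not having resumed. The figure is then r(N − f)/N, which for N = 70 and r = 0.30 is 28%, 27% and 26% at f = 4, 7 and 10. It falls as more people fail to stop.

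**Effect on the bleeding rate under the hypothetical estimand.** The planning rates (Protocol 10.1) are 3 for SoC and 0.85 for Roctavian, a ratio of 0.85/3 = 0.283. Assume stoppers bleed at 0.85, never-stoppers at rate A, and equal time per person. With p the never-stopped share, the all-recipient ratio is ((1 − p) × 0.85 + pA)/3.

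| p | A = 3 | A = 5 |
|---|---|---|
| 5% | 0.319 | 0.353 |
| 10% | 0.355 | 0.422 |
| 20% | 0.427 | 0.560 |

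If never-stoppers, protected by prophylaxis, bleed less than 0.85, the shift reverses: at p = 10% and A = 0.5 the ratio is (0.765 + 0.05)/3 = 0.272.

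**Effect on power.** The sample size formula in SAP 7.6 (rate ratio margin 0.5, one-sided 2.5%, 80% power, ratio 0.2, 1 year, overdispersion 1.5) has V1 = 1/3 + 1/(0.2 × 0.85) + 9 = 15.216 and V0 = 1.21/0.317 + 9 = 12.817. Then N1 = (1.960√12.817 + 0.842√15.216)²/0.568² ≈ 328.8, rounded up to 329, with N2 = 66. The total of 395 agrees closely with the stated 397. At 330 and 67, power is 80.6%. Losing 3, 7, 10 or 13 recipients lowers it to 79.1%, 77.0%, 75.3% or 73.4%.

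**The case against.** The strongest reply is that these people are already analyzed. The treatment policy estimand follows every recipient from index, the G-BA required it, SAP Annex 12.1 fills all shells for it first, and SAP 7.9.3 starts bleeding-rate follow-up at index for both cohorts. Consistency between the estimands is to be discussed in every report. This stands, so nobody is lost to the study. It does not repair Protocol 10.3.7.6, whose denominator is restricted whatever the estimand.

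A second reply is that the hypothetical estimand aims to minimize time under both treatments, and all of a never-stopper's time is of that kind. That is a fair account of the target. It explains the exclusion, but the plan still states no rule and reports no count for it.

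Three stronger readings are tempting, and the documents do not support them:

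- A reader might infer that both analyses cover responders only. They do not: people who stop and later return are the events in the objective, and they contribute hypothetical-estimand time until resumption.
- A reader might infer that the bleeding comparison is biased towards Roctavian. The direction depends on how never-stoppers bleed while on prophylaxis, which is unknown.
- A reader might take the SAP 7.9.4.6 population literally as the whole cohort, since all continue prophylaxis at first. Read with SAP Table 5, which uses the registry's return question and return date, it more naturally means those who returned. The wording still differs from the protocol's.

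**Conclusion.** The point holds in limited form. By stated rule, never-stoppers are outside the return-to-prophylaxis objective, and they have no defined entry for bleeding and hemostatic-use outcomes under the hypothetical estimand. The omission understates the share of recipients on continued or resumed prophylaxis. It also understates hemostatic use under the hypothetical estimand, because those left out are on routine prophylaxis throughout. For the bleeding rate neither direction nor size is established.

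All magnitudes above rest on assumed never-stopped and return rates; if nobody fails to stop, the effect is nil. No figure in the plan is wrong. The change is worth making because it alters what the durability result says, at little cost.

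**What to change.** In Protocol 10.3.7.6 and 7.2.5.2, and in SAP 7.9.4.6 and Table 18:

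- Use all infused participants with adequate follow-up as the denominator for the proportion still on, or returned to, prophylaxis.
- Report those who never ended prophylaxis as a separate row.
- Keep the time-to-resumption summaries for those who stopped. Do not enter never-stoppers as resumptions at time 0, which would distort the planned mean, median and minimum.
- At interim cuts, show recent recipients still in the initial prophylaxis period separately.
- Reconcile the populations in these sections so that one definition applies.

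For the hypothetical estimand (Protocol 10.3.2.3, SAP 7.2.3), state how never-stoppers are handled, and report the number and baseline profile of infused participants who never enter. Add one sensitivity analysis that includes them from week 5 with their observed bleeds and FVIII use, keeping the planned start and censoring for everyone else. It isolates this selection, whereas the treatment policy analysis also changes the start and censoring for the other recipients; the two should be read together. SAP 7.3.3.2 places the 3-day and 27-week offsets before the end of prophylaxis where SAP 7.2.3 places them after, and this should be reconciled in the same edit.

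The cost is wording, one table row and one extra run. The registry fields for therapy dates and return to prophylaxis already exist. None of this bears on when prophylaxis should be stopped.
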